### **Objective 2: Mediator/Moderator Analyses.**

**Examination of intervention mechanism.** Consistent with our theoretical model and based on our prior studies and literature review, we hypothesize that FN intervention effects will be mediated by parents' capacity to pursue services, access to services, and structural barriers. We will examine mediational effects using two different, but related, methods: the approach of Baron and Kenny and the use of path analysis models. Each approach can be used to differentiate between direct and indirect intervention effects. In the path analysis models (which have greater statistical power), we will create a series of nested models based on our theoretical model in which we will systematically vary model parameters and constraints to test the effect of each potential mediator. Nested models will be compared using difference tests and other standard indices (Akaike's Information Criterion, the comparative fit index (optimal value > 0.95), the Tucker-Lewis index (optimal value > 0.95), and the root mean square error of approximation (optimal values < 0.06)). We will fit these models with MPlus software, which allows for the modeling of continuous and dichotomous, endogenous, and exogenous variables. While our study design only allows for direct testing of the causal effects of primary delivery strategies A, B, C, the causal effect of mediating variables can be analyzed by treating factors as instrumental variables in the path analysis. Results will directly inform choice of final variables for statistical process control charts to be refined in Aim 3 and investigated in future studies as a quality control method.

**Moderator analyses.** We will evaluate the extent to which each delivery strategy, race/ethnicity, primary language, and symptom severity moderate FN effects using stratified analysis. Previous studies have found no effect of such demographic variables on the effect of FN. We hypothesize that any effects will be small and clinically non-significant yet will perform these analyses as evaluation of moderators is important to ensure equity.

**Approach to missing data.** Given our reliance on EHR and billing records rather than self-report to assess primary outcomes, we anticipate relatively little incomplete data in primary analytic variables. Nevertheless, initial analyses will also compare participants with complete data with those who are missing outcome data. We will explore and summarize the extent of incomplete data and use multiple imputations if they are deemed appropriate. Such methods allow for the calculation of unbiased estimates despite many types of missing data.

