Design/Methodology:	
We will be using a highly efficient experimental design to identify which of the FN components contribute meaningfully to improvement in the primary outcome - access to child mental health services. We will concurrently gather information on FN's mechanisms of effectiveness. The study will take place in the real world context of a community health care center.
 
Children will be enrolled if they have a positive behavioral health screen on one of the age appropriate screening measures (PSC or PPSC) which are universally used in the clinic OR parent report of a behavioral health concern. If agreeable, families will be referred to a FP who will inform families about the study. Families who consent to study participation will be randomized to one of 16 combinations of strategies to deliver FN and will work with the study FP. Families who decline participation in the study will have the option to work with health center care managers (instead of the study FPs) who also offer care coordination. Those families will not be randomized or followed as part of the study.
 
Delivery of FN will be systematically varied across four components, each of which is represented by a separate factor in our 2x2x2x2 factorial study design (See figure 1). Specifically, each family (includes parent/legal guardian, child and if applicable, additional siblings) will be randomly assigned to one of two conditions within each of 4 factors or delivery strategies, defining 16 separate experimental conditions. Strategies include: (A) technology-assisted delivery of care coordination using an innovative, web-based platform called Act.MD (compared to usual care); (B) clinic based FN + community-based (compared to clinic-based only); (C) enhanced symptom tracking using more frequent behavioral symptom tracking by the FP (compared to standard pediatric surveillance); and (d) individually tailored vs standardized, schedule-based visits with families. All children will be followed through the EHR for 12 months, for outcomes in services access and symptom tracking.

We will estimate main effects of the 4 experimental factors and the effects of combinations of the delivery strategies on the study's primary outcome – family engagement in child mental health services.

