### **12.2 Sample Size Determination**

#### **Sample Size and Power.**

Of the three measures to operationalize engagement, we powered our study on the dichotomous variable “receipt of BH services within 90 days” - the most conservative estimate. We base our power calculation on the number needed to detect the smallest differences in primary outcomes that are of clinical importance. Our formative work with staff at DotHouse and other community health centers indicates that a relative risk of approximately 25% would be considered clinically significant. Therefore, if 60% of families in the core navigation condition engage in mental health services (estimates based on our prior work), to detect a 25% difference (i.e. 75% of families in any of the FN delivery conditions engage in services), and assuming 2-tailed tests and a type 1 error rate of 5%, approximately 304 participants are required to detect this effect (n=38 in each of 8 cells). Although 304 participants are required for our power analysis, we will be enrolling 715 human subjects which include 304 parent/legal guardian, 304 index children for primary analysis and around 107 siblings for families with more than one eligible child. Additional sibling analysis will be done to explore differences in service goals etc.

We expect strong effects of study mediators, in particular fidelity variables and variables that are central to our theoretical model, such as increased parent capacity. Following published guidance based on an empirical review, we estimate that our design will have at least 80% power to detect mediation effects where the paths from independent variable to mediator and from mediator to outcome are of at least small-to-medium effect (ES=.26). Given that our mediation analyses are designed to support decisions regarding intermediate outcomes to be tracked for quality control and assurance, effect sizes less than this magnitude are not considered to be clinically important. In contrast, analyses of patient-level treatment moderators are exploratory as we have no evidence to support hypotheses of any effect.

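### Mediation analysis: no test of the indirect effect or deciding rule is specified, and the Baron and Kenny steps cannot reach the stated 80% power at the trial's own design effect

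*Combined protocol and SAP*

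**What the plan says.** Section 12.3 (Objective 2, examination of intervention mechanism) gives the methods: "We will examine mediational effects using two different, but related, methods: the approach of Baron and Kenny and the use of path analysis models". It adds that the path models are the more powerful of the two. They are to be a nested series in which parameters and constraints are varied to test each mediator. On how they are judged: "Nested models will be compared using difference tests and other standard indices". The indices listed are AIC, CFI, TLI and RMSEA, the last three with optimal values.

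Section 12.2 states: "we estimate that our design will have at least 80% power to detect mediation effects". The condition is that both paths, factor to mediator and mediator to outcome, are at least 0.26. It gives no test, no metric for the 0.26, no outcome scale and no size for any direct effect.

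Neither section names a product-of-coefficients test, a bootstrap, or a confidence interval for the indirect effect. Neither says which constraint, when rejected, counts as mediation, or what follows if the two methods disagree.

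**The concern.** Baron and Kenny in its classical form asks for three significant results: the total effect of the factor on the outcome, the factor-to-mediator path (a), and the mediator-to-outcome path given the factor (b). The first is not a test of mediation. When the mediator carries the whole effect, the total is only the product of the two paths, 0.26 x 0.26 = 0.068, which 304 families can rarely detect. A real mediator can therefore fail under one planned method and pass under the other, and nothing in the plan settles the disagreement.

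Mechanisms are part of the secondary objective (section 4.1). Section 12.3 also says these results will guide the choice of variables for the quality-control charts. A variable could be left out because of the method read rather than because of the data.

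**Working it through.** **Inputs.** From section 12.2: outcome "receipt of BH services within 90 days" (binary); the control rate, "if 60% of families in the core navigation condition engage in mental health services"; 75% under an enhanced condition; two-sided 5%; "approximately 304 participants are required to detect this effect"; both mediation paths 0.26. From section 2: each family "will be randomly assigned to one of two conditions within each of 4 factors or delivery strategies". Assumed here: 1:1 allocation within a factor (152 v 152), an overall outcome rate of 67.5%, no missing data, and 0.26 read as a standardised path.

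**1. The plan's sample size.** Per level, n = [1.96 x sqrt(2 x 0.675 x 0.325) + 0.842 x sqrt(0.60 x 0.40 + 0.75 x 0.25)]^2 / 0.15^2 = [1.96 x 0.662 + 0.842 x 0.654]^2 / 0.0225 = 151.9. This rounds to 152, or 304 in all. Power at 152 v 152 is 80.0%, so the plan's figure reproduces.

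**2. A ceiling that needs no simulation.** The total-effect step of Baron and Kenny is this same comparison. At 60% v 75% it has 80.0% power. Requiring a and b as well can only lower that.

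**3. Size of the shortfall.** Simulation with 4,000 runs per setting: factor coded -1/+1, linear regression for the mediator, logistic regression for the outcome. The outcome was generated from a latent probit with b = 0.26, or from the equivalent logit, b = 0.26 x pi/sqrt(3) = 0.472. Ranges cover the two generating models.

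| Setting, n = 304, binary outcome | Baron and Kenny | a and b jointly significant | Sobel product test |
|---|---|---|---|
| No direct effect (logit margins about 65% v 70%) | 13-15% | 92-95% | 88-91% |
| Direct effect set to give 60% v 75% | 73-76% | 92-95% | 88-91% |

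Multiplying the simulated power of the three steps (total, a, b) gives the same answers:
- 60% v 75%, probit: 0.794 x 0.996 x 0.926 = 0.73.
- 60% v 75%, logit: 0.807 x 0.998 x 0.948 = 0.76.
- No direct effect, logit: 0.154 x 0.997 x 0.950 = 0.15.

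The total-effect step is what limits the procedure.

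**4. Continuous outcome.** With no direct effect the total is 0.0676. Then z = 0.0676 x sqrt(304) / sqrt(1 - 0.0676^2) = 1.18, and power for the total is P(Z > 1.96 - 1.18) = 22%. In simulation Baron and Kenny has 22% and joint significance 99%.

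**5. Where Baron and Kenny does pass 80%.** On the binary outcome it needs a larger total effect than the trial was sized on: a direct effect of 0.20, about 58% v 77%, gives 89%. On a continuous outcome a direct effect of 0.10 gives 84%.

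**6. Other readings of 0.26.** Binary outcome; the Baron and Kenny range runs from no direct effect to 60% v 75%.

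| Reading | Joint significance | Baron and Kenny |
|---|---|---|
| Standardised paths | 92-95% | 13-15% to 73-76% |
| Path a is a two-group difference of 0.26 SD (0.13 on the -1/+1 coding) | 59-61% | 5-6% to 49-50% |
| Path b is a log-odds of 0.26 per SD | 50-53% | 4-5% to 39% |
| Both of the last two together | about 34% | about 2% to 28% |

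On the second reading path a alone has z = 0.13 x sqrt(304) / sqrt(1 - 0.13^2) = 2.29, which is 63% power.

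**The case against.** A reader might infer that mediation is to be judged only by Baron and Kenny and global fit indices, and that the 80% statement is therefore false. The documents do not support either inference.

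- Section 12.3 lists difference tests first, on models built to test each mediator. Separate constraints a = 0 and b = 0, both rejected, would amount to joint significance, with 92-95% power under standardised paths. A single two-degree-of-freedom test of a = b = 0 would not test mediation, and dropping the direct path would test the direct effect. The plan does not say which is meant. The gap is in the constraints and the decision rule.
- Section 12.2 attaches the 80% to the design, citing published guidance, and not to Baron and Kenny. Section 12.3 already concedes that the path models have more power. Under standardised paths the 80% holds for joint significance and for the Sobel test.
- The low power of Baron and Kenny comes from its total-effect step. The fit indices play no part in it.
- Error rates can be worked out for an RMSEA cut-off in a model with one factor, one mediator and one degree of freedom. They do not carry over, because the plan has several factors and mediators and calls its index values optimal without making them an accept-or-reject rule.

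These points stand, and they limit the finding. So does a point about timing. In Table 2 parental attitudes and family resources are first re-measured at 6 months and the PHQ-2 at 3 months, at or after the 90-day window. The simulation takes the mediator to come before the outcome, and no choice of test repairs that order.

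It is also fair to say that Baron and Kenny could be kept as a descriptive supplement, and that this is a secondary objective feeding charts still to be refined. Neither answers the missing deciding rule or the undefined metric.

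**Conclusion.** The point holds in a limited form. The plan specifies no test or interval for the indirect effect and no rule for declaring a mediator. One of its two named methods must fall short of 80% power at 60% v 75%; that result follows from the plan's own sizing and needs no assumption about paths.

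The size of the shortfall does rest on assumptions that the documents do not give: standardised latent-scale paths of 0.26, all 304 families analysed, the 90-day binary outcome, and a direct effect between zero and the value that yields 60% v 75%. On those terms Baron and Kenny has about 14% to 76% power, against 92-95% for joint significance.

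The 80% statement is unanchored rather than refuted. It is met for a test of the indirect effect if 0.26 is a standardised path. It is not met, at about 50-61%, if 0.26 is a two-group difference for path a or a log-odds per SD for path b. It cannot be checked until the test, the metric and the outcome scale are named. The matter should be corrected, but it does not touch the primary analysis.

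**What to change.** In section 12.3:
- Make the deciding test for each mediator the indirect effect (product of the two paths) from the path model, with a bootstrap confidence interval, adjusted for the baseline value of the mediator where one is collected (Table 2 shows baselines for the questionnaire measures).
- Drop the requirement of a significant total effect, and keep Baron and Kenny as descriptive at most.
- Use AIC, CFI, TLI and RMSEA to describe model fit, not as evidence of mediation.

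In section 12.2, restate the mediation power for that test, giving the metric of 0.26 for each path and the outcome scale, and change the figure if it does not hold. Simply attaching the present 80% to the new test would not be safe. The bootstrap itself was not simulated here; joint significance and Sobel stand in for it.

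The cost is wording and a little more analysis in Mplus, which the plan already names. No new data are needed. The stated power may come out less favourable.

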**Table 2. Theory-based Mechanisms and Measures**

Domain	Target	Theoretical	Instrument	Description	Timing
Person	Parent capacity	Improved parental attitudes about mental health increases capacity to engage in services	Parental Attitudes Towards Psychological Services Inventory	26-item questionnaire to assesses mental health attitudes and stigma	Baseline, 6, 12 months
	Parent capacity	Improved parent mental health increases capacity to engage in services	Patient Health Questionnaire-2	Validated 2-question depression screener	Baseline, 3, 6, 9, 12 months
Systems	Access to resources	Improving social determinants increases access to resources	Family Resource Scale	30 items assess adequacy of resources	Baseline, 6, 12 months
	Overcome barriers	Coordination decreases structural barriers	Electronic Health Record FP Templates	Contains resource use and care coordination activities	Monthly data reports

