## 8. Study Intervention: Family Navigation

Family navigation (FN) is care management designed to address barriers to services – in our study, behavioral health services. In this study, the core FN intervention will be delivered to all participants by study Family Partners (FP), a paraprofessional community member who is trained to support families of children with behavioral health. FN strategies to be tested will be delivered. Literature strongly supports the hypothesis that initiation of behavioral health services is directly influenced by several key domains, including: parents' motivation and capacity to pursue services (e.g., health literacy, mental health), families' resources and competing demands on their time, and healthcare system factors, such as difficulties scheduling timely appointments and barriers to communication. Core FN components (see Figure 4) are designed to address these domains. For example, motivational interviewing is included

to increased parents' motivation to pursue services. Problem-solving strategies are introduced to improve parents' capacity to pursue services, and education addresses health literacy. Assistance with social determinants of health is essential for reducing competing demands on families' time (e.g., help with housing, benefits). Care coordination is focused on healthcare system factors and is designed to promote an activated care team. The components of the core navigation intervention, which all participants will receive, are described below.

Of note, the core FN intervention exceeds the current standard of care at the health center. Dothouse

employs care managers who assist families access behavioral health services and meet concrete resource needs. However, care managers are not routinely involved with all children with behavioral health concerns and they do not support engagement longitudinally.

- Universal Screening and Behavioral Health Referral. As described above, The FN intervention begins with a family-centered response to a positive behavioral health screening or parent report of a concern. The FP will provide psychoeducation and use MI to explore family preferences regarding further evaluation, and referral to behavioral health services.

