family, they would like services and would like to work with the FP, the family will have the opportunity to enroll in the study and be randomized to a study condition. This group of parents will be called the “watchful waiting” group. The watchful waiting group will NOT be consented at the time of initial contact. If they are interested in pursuing services for their child at the time of recontact, the parent and child will be offered study participation at that time and will have the opportunity to consent to or decline participation. We have included this group based on our clinical experience. We find that many families wish to delay services for a number of reasons including life events (family moving, expecting a new baby) and timing (child going away for the summer, want services through school and school ending or not in session). We would like to make study participation available for such families.

The FP will administer the baseline assessment measures and then the family will be randomized (on an individual basis through a randomization generator centralized with the study statistician) to a study condition. If the family declines participation, the FP will refer the family to health center care managers and have no further contact with the family.

**Randomization Procedures.** Before initiation of FN, FPs will assign each family an experimental condition using a computer program. The computer program will use both a randomly-generated number and “minimization procedures” to minimize imbalances across conditions with respect to target variables, including family/child characteristics (e.g., education, gender, race/ethnicity, screening score). In this procedure, the first participant is assigned at random. Subsequent participants have a p chance of being randomly assigned and a 1-p chance of being automatically assigned to the condition that would most reduce imbalance based on selected sample characteristics. Minimization procedures are considered best practices for sequential assignment. Families with more than one child enrolled will participate in the same random condition for all children.

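### The mediation models specify no baseline mediator value, although three mediators are scheduled before randomisation, so the mediator-to-outcome path can credit pre-existing family differences to a mechanism

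*Combined protocol and SAP*

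**What the plan says.** Section 12.3, Objective 2, names two ways to study mechanism: the Baron and Kenny approach, and a series of nested path models "in which we will systematically vary model parameters and constraints to test the effect of each potential mediator". It also says the factors may serve as instruments for the mediators. No covariate is named for any of these models. By contrast, the Cox models under Objective 1 do name one.

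Table 2 gives the PHQ-2 schedule as "Baseline, 3, 6, 9, 12 months"; the attitudes inventory and Family Resource Scale are set for baseline, 6 and 12 months. Section 9 fixes the order: "The FP will administer the baseline assessment measures and then the family will be randomized". In Section 12.3, baseline values appear only in the balance comparison, and these three mediators are not among the characteristics listed there.

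Section 12.2 claims at least 80% power for mediation when the "paths from independent variable to mediator and from mediator to outcome are of at least small-to-medium effect (ES=.26"). Section 12.3 says the results will guide which variables go onto the process control charts.

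**The concern.** Randomisation protects the factor-to-mediator path. It does not protect the mediator-to-outcome path, because nobody is randomised to a level of attitudes, mood or resources. Section 8 states that "initiation of behavioral health services is directly influenced by several key domains", and names parents' motivation and capacity and families' resources among them. On that premise, the level a family brings to the trial helps determine both its later score and whether it reaches services. A model without the baseline score gives that shared origin to the mechanism.

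At stake is the choice of quality-control variables. If a factor shifts a score that does nothing for engagement, the trial could still name the score as a mechanism and recommend tracking it.

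**Working it through.** **Inputs from the documents.** 304 families, so 152 per level of each factor; two-sided 5%; engagement 60% against 75% (Section 12.2); path size .26 (Section 12.2); outcome at 90 days from randomisation (Section 4.2.1); mediator schedule (Table 2).

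**Inputs assumed.** ρ, the correlation of a mediator's baseline and follow-up scores: 0.3, 0.5, 0.7. r, the correlation of the baseline score with engagement: about 0.14 and 0.25. The documents give neither.

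**The plan's own figures.**
- Sample size, with 80% power assumed because none is stated for this calculation: n per level = [1.96√(2 × 0.675 × 0.325) + 0.842√(0.6 × 0.4 + 0.75 × 0.25)]² / 0.15² ≈ 152, total 304. It reproduces.
- Mediation power with .26 as a standardised path: z = 0.26/√((1 − 0.26²)/304) = 4.70; power per path Φ(4.70 − 1.96) = 0.997; both paths 0.997² = 0.99. The claim of at least 80% holds.
- With .26 as a between-level mean difference in SD units, the factor-to-mediator test alone has Φ(0.26√76 − 1.96) = 62%. Only the path reading supports the stated power.

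**Where the bias comes from.** Let M1 = 0.26A + ρM0 + error, with A = ±1 (a 0.52 SD difference between levels), and let engagement Y depend on M0 only. The true mediator effect is then zero.
- Without M0, the correlation of M1 and Y given A is ρr/√(1 − 0.26²) = ρr/0.966, which is not zero.
- With M0 in the model it is zero.

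Approximate rejection rate without M0: Φ(√304 × ρr/0.966 − 1.96). For ρ = 0.5 and r = 0.25 this is 17.44 × 0.129 − 1.96 = 0.30, so 62%.

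**Simulation of the joint-significance test** (both paths significant, null mediator, engagement averaging 67.5%, no factor effect on engagement):

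| r | ρ = 0.3 | ρ = 0.5 | ρ = 0.7 | With baseline |
|---|---|---|---|---|
| about 0.14 | 11% | 23% | 40% | about 5% |
| about 0.25 | 27% | 59% | 89% | about 5% |

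The closed form agrees closely. A second set of runs, expressed as the odds ratio per SD of baseline score, gives 8% at odds ratio 1.25 and ρ = 0.3, rising to 96% at odds ratio 2.0 and ρ = 0.7. The rate is about 5% if baseline does not predict engagement, and at or below 5% if the factor does not move the mediator.

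**Baron and Kenny with a total-effect step, no baseline value.** If the factor has no effect on engagement, the rate is at or below 5%. If the factor raises engagement from 60% to 75% by another route, it is 19% / 43% / 65% at ρ = 0.3 / 0.5 / 0.7 with r about 0.25, and about 9% in the weakest setting.

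**Instrumental variable, no baseline value.** About 3% false positives if the factor has no direct effect on engagement; about 71% to 72% if it has the planned effect directly.

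**Precision of the factor-to-mediator path.** The unadjusted standard error is larger by 1/√(1 − ρ²), that is 5% / 15% / 40% at ρ = 0.3 / 0.5 / 0.7. On the mean-difference reading, adjustment lifts power from 62% to 66% / 74% / 89%. On the path reading, power already exceeds 99%.

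**Timing.** Attitudes and family resources are first re-measured at 6 months, after the 90-day outcome is settled. If receiving services itself shifts the later score by an assumed 0.3 SD, joint significance still declares false mediation in 71% to 95% of trials with the baseline value in both equations.

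**The case against.** The plan is silent; it does not exclude baseline values. Its hypotheses are worded as improvement over time, and an analyst might well adjust. That stands: the defect is that the adjustment is not specified, and a reader who infers that the models forbid it goes beyond the text.

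A reader might also take the upper simulated figures as the error rate of the plan as written. The documents do not support that. Section 12.3 names no joint-significance rule, and Baron and Kenny, which it does name, conventionally asks for a total effect first. That step protects when the factor does not affect engagement, but not when the factor works by another route, which is the case in which mechanism matters.

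The instrumental-variable sentence is a fair reply to confounding, but it is valid only if a factor acts on engagement solely through the mediator. The same section sets out to separate direct from indirect effects, so it cannot assume this throughout.

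Two further limits stand. The correlations are assumed; Section 8 supports their direction only. And these are secondary analyses, whose control-chart variables are still to be refined and studied later.

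**Conclusion.** The point holds as an omission in the mediation models. Where a factor moves the mediator and the baseline score predicts engagement, the unadjusted mediator-to-outcome path is biased. Under the assumed ranges, a null mediator is declared a mechanism in about 11% to 89% of trials by joint significance. With the total-effect step the range is about 9% to 65% if the factor has its planned effect by another route, and at or near 5% if it has none.

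Two stronger readings fail. Loss of precision is not a main harm: it matters only if .26 is a mean difference, and the stated power fits the path reading. Nor does baseline adjustment make the mediation results sound for all three questionnaires. It removes baseline confounding only; for the 90-day outcome, reverse causation remains for attitudes and family resources. Nothing here touches the primary factor effects.

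**What to change.** In Section 12.3, Objective 2, state that for each mediator with a baseline assessment (attitudes inventory, PHQ-2, Family Resource Scale) the baseline value enters as a covariate in both the factor-to-mediator and the mediator-to-outcome equation, in every Baron and Kenny regression and every path model. State how missing baseline forms are handled, for example by full-information maximum likelihood. The log-based coordination measure has no baseline and stays as it is.

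Confirm that the attitudes inventory is collected at baseline: Table 2 lists it, but the measures list in Section 9 and Appendix A do not.

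Deal separately with the order of the 6-month mediators and the 90-day outcome, and say under what assumption the instrumental-variable analysis will be read.

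The cost is a few sentences and one covariate per model. PHQ-2 and family resources need no new data; the same is true of attitudes if the baseline is confirmed.

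### For race/ethnicity, primary language and symptom severity the plan offers only stratified analysis, which neither tests nor quantifies a difference in effects

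*Combined protocol and SAP*

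**What the plan says.** The moderator paragraph in Section 12.3 (Objective 2) reads: "We will evaluate the extent to which each delivery strategy, race/ethnicity, primary language, and symptom severity moderate FN effects using stratified analysis". It adds that any moderation is expected to be small and not clinically important, and that the analyses are done for reasons of equity. For race/ethnicity, language and severity, the documents give no interaction term, no test of homogeneity and no rule for comparing strata.

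Two other places bear on this:

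- Section 12.2 limits the status of the work: "analyses of patient-level treatment moderators are exploratory as we have no evidence to support hypotheses of any effect".
- Section 12.3 (Objective 1) says that interactions among the delivery strategies will be explored with effect coding. When the moderator is another delivery strategy, interaction modelling is therefore already planned.

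The question of whom the intervention works for is a stated secondary objective (Section 4.1) and has its own heading as Objective 2a (Section 4.2.2).

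**The concern.** Moderation is a difference between effects. Fitting the model separately in each stratum gives several effects, each with its own precision, and leaves the comparison to the reader. Precision differs with stratum size. A common effect can therefore reach significance in a large group and miss it in a small one.

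At stake is the message on equity. Enrolment is expected to be 84% ethnic-racial minority, and the investigators themselves expect little true moderation. The error to guard against is a report that a strategy helps one racial or language group and not another when the effect is the same. The primary conclusions do not depend on these analyses.

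**Working it through.** **Inputs.** All are from Section 12.2 unless noted.

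- Reference rate: "if 60% of families in the core navigation condition engage in mental health services".
- Enhanced rate: "75% of families in any of the FN delivery conditions engage in services".
- Test: "assuming 2-tailed tests and a type 1 error rate of 5" per cent.
- Size: "approximately 304 participants are required to detect this effect (n=38 in each of 8 cells"). 38 × 8 = 304, and 19 × 16 = 304 for the 16 conditions of the current design.
- Allocation (Section 2): each family is "randomly assigned to one of two conditions within each of 4 factors or delivery strategies". Taking this as 1:1 gives 152 families per level of each factor.
- Power for the primary comparison is not stated. The only figure is for mediation: "we estimate that our design will have at least 80% power to detect mediation effects".
- Subgroup shares: only the 84% minority share is given (Section 2). The other splits below are assumptions.

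**Step 1: reproduce the plan's figure.** With pooled variance and no continuity correction,

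n per level = [1.960·√(2p̄(1−p̄)) + 0.842·√(p₁(1−p₁)+p₂(1−p₂))]² / (p₂−p₁)², with p̄ = 0.675.

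This is [1.960 × 0.6624 + 0.842 × 0.6538]² / 0.15² = 152, so 304 in total. The plan's figure is reproduced at 80% power (80.0% at 152 per level).

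**Step 2: power within a stratum.** For m families per level in a stratum,

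power = Φ{[√m·(p₂−p₁) − 1.960·√(2p̄(1−p̄))] / √(p₁(1−p₁)+p₂(1−p₂))}.

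Two equal strata have m = 76: Φ[(1.3077 − 1.2982)/0.6538] = 50.6% in each. With an 84/16 split, power is 72.8% in the larger stratum and 19.6% in the smaller.

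**Step 3: chance that exactly one of two strata is significant, the true effect being identical.** This is A(1−B) + B(1−A), where A and B are the two powers. For equal strata at the design effect: 2 × 0.506 × 0.494 = 50.0%. With no effect: 2 × 0.05 × 0.95 = 9.5%. Each entry gives the formula result, then a simulation of 400,000 trials.

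| Split | 60% v 75% | 60% v 70% | 60% v 65% | No effect (60% v 60%) |
|---|---|---|---|---|
| 50/50 | 50.0% / 50.0% | 37.6% / 38.1% | 16.8% / 18.4% | 9.5% / 10.2% |
| 70/30 | 55.0% / 54.9% | 38.9% / 39.3% | 16.8% / 17.7% | 9.5% / 9.2% |
| 84/16 | 63.8% / 64.0% | 41.2% / 41.5% | 16.9% / 18.0% | 9.5% / 9.8% |

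With more than two strata, the chance at the design effect that they do not all agree is 69% for three equal strata and 73% for four.

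**Step 4: the interaction test on the same data.** A Wald test of the difference in log odds ratios rejected in 4.8% (50/50), 4.7% (70/30) and 4.1% (84/16) of simulated trials at 60% v 75% in both strata. Over all scenarios in the table the range was 4.1% to 5.0%.

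**Step 5: what the interaction test can detect.** Suppose the 15-point effect exists in one half (60% v 75%) and is zero in the other (60% v 60%). The difference in log odds ratios is ln 3 − ln 1.5 = 0.693. Its standard error is √[3/(76 × 0.24) + 1/(76 × 0.1875)] = 0.484. Power is Φ(0.693/0.484 − 1.96), about 30%. On the risk-difference scale it is about 28%.

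**The case against.** A reader might infer that the plan will declare moderation whenever one stratum is significant and another is not. The documents do not say so. Stratified analysis can also mean stratum-specific estimates with intervals, or a test of homogeneity. The disagreement rates in the working therefore describe one possible way of reading the strata. This objection stands, and it is why the criticism is that the comparison is unspecified. It does not supply the missing comparison.

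A reader might also infer that interaction modelling is absent altogether. It is not: Objective 1 covers strategy-by-strategy interactions, so the point is confined to the three patient-level moderators.

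The consequence is limited too. Section 12.2 calls the patient-level analyses exploratory, and the stated expectation of little moderation works against over-reading a discordant stratum. This lowers the priority of the point. It does not turn separate estimates into an assessment of their difference.

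Finally, the remedy has a weakness of its own. At about 30% power for a large difference, an interaction test will miss most real ones, and for an equity question a missed difference matters as much as a false one. That is a reason to put the weight on the interval. Separate strata have no more information about the difference.

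**Conclusion.** The point holds for race/ethnicity, primary language and symptom severity: the named method does not test or quantify what the objective asks. This follows from the text and needs no arithmetic.

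The size is conditional. It is tempting to say that equal effects will look different about half the time. The documents do not support that as a general statement. It requires strata to be read by significance, two roughly equal strata, and the full 15-point effect in both. Section 12.2 presents 15 points as the smallest difference of clinical importance, not as a forecast for every factor. Under the significance reading, the rate for two strata runs from about 10% with no effect to 64% at the design effect with an 84/16 split. Even the lowest value is about twice the 5% of an interaction test, and the gap is widest when a strategy works.

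The change is worth making because it is cheap and serves a stated secondary objective.

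**What to change.** In Section 12.3, replace stratified analysis as the method for these three moderators with the following:

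- For each factor, add the moderator's main effect and the factor-by-moderator term to the Objective 1 logistic model for receipt of services within 90 days.
- For race/ethnicity, which has several categories, use one joint test with the corresponding degrees of freedom.
- For severity, use the baseline score standardised within instrument, because children aged 3-5 have the PPSC and those aged 6-12 the PSC-17. This also avoids a cut-point.
- Report every interaction estimate with its confidence interval, labelled exploratory. Show stratum-specific estimates as description only.
- State that power is low (about 30% in the case worked above) and that a non-significant interaction will not be taken as evidence of equal effects.

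The cost is a few sentences, plus fixing the categories for race/ethnicity and language in advance. Data, sample size and software are unchanged.
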